2. **Randomization and blinding:** The study has a blinded and randomized design. A randomization code will be generated prior to recruiting and patient randomization will be assigned accordingly. Since we expect a larger dropout in the KD group, we pre-set the ratio of KD:SA participants as 3:2 in the randomization generation.* Nurses and research staff who do CIWA, craving ratings and other study procedures with patients will not have access to the randomization key. An independent person (BSN RN) will perform and analyze daily ketone testing and blood pricks and will have access to the key. The nutrition department also has access to the randomization key to prepare the diets, but patients' diets will be sent out without information on its contents.* This ratio will be set for the first 20 participants. After the enrollment of 20 participants, the ratio will be evaluated by an independent person (BSN RN) based on diet compliance during their 3 weeks inpatient stay as per questionnaire and urine screen. Results are shared with the PI who will modify the ratio if needed to aim for a 50% KD versus 50% SA study completion.
3. **Diet Compliance:** In addition to daily urine tests (described above in section 4.e.1) and blood pricks, a daily questionnaire on whether additional food was consumed and whether the participant was compliant will be assessed by an independent person (BSN RN). On each day, participants will be asked if they were compliant to the diet (i.e. the shakes and snacks provided), or if additional food was consumed. If yes, which food items and at what time. At that time, they will also be encouraged to be compliant with the diet. All participants will be motivated on a daily basis to be compliant to their diet by nutrition department staff. If after the first 3 days of diet initiation a participant (in either KD or SA) self-reports non-compliance to the diet for 4

days, the PI will be informed and participant will be withdrawn and excluded from further study participation.

Additionally, if after the first 5 days of diet initiation, a participant in the KD group has 3 urine tests that are negative for ketone bodies, this participant will also be removed from the study. In this case, the independent person who monitors daily urine testing, will inform study staff about the compliance breach and the patient will be removed from the study.

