Empirical knowledge regarding the necessary sample size for significant effects of a ketogenic diet on withdrawal, NP or brain functioning in AUD during withdrawal does not exist. Previous behavioral and pharmacological treatment studies in AUD with behavioral, fMRI and MRS as outcome measures have studied on average 20-25 patients per group [treatment versus control: reviewed in 109]. Clinical efficacy of a ketogenic diet in epilepsy was established in randomized-controlled trials in 20 [55] or 94 epilepsy patients [56]. In 20 elderly participants, an acute dose of ketogenic meal improved executive functioning 1.5-3 hours after, as compared to a control meal on a different day [58]. Further, beneficial effects of KD on sleep was established in a study in 18 children with epilepsy [57]. Thus, for within-subject fMRI studies in individuals with AUD sample sizes of 25 patients per group have been effective for obtaining interpretable data regarding behavioral and neurocognitive effects of treatment, suggesting that the sample size of the current protocol is adequate for the identification of effects of ketogenic diet in AUD.

Independent sample t-test will be used to test **Hypothesis 1**, “withdrawal symptom severity within the first week of detoxification will be lower for patients with KD compared to control diet”.

Paired t-test on BOLD signals will be used to test **Hypothesis 2**, “limbic activation to alcohol cues would be reduced after 3 weeks of treatment”; **Hypothesis 3**, “the functional connectivity of the saliency network will be stronger after 3 weeks of treatment”; **Hypothesis 4**, ‘prefrontal cortex atrophy and ventricular enlargement will stronger decrease after 3 weeks of KD treatment compared to control diet’. Assuming a threshold probability for rejecting the null hypothesis (Type I error rate), $\alpha = 0.05$, and a probability of failing to reject the null hypothesis under the alternative hypothesis (Type II error rate), $\beta = 0.2$, the

proposed sample sizes (25 KD versus 25 ND) will allow us to detect an effect size of 0.66.

To test KD treatment effects, mixed ANOVAs will be used to assess whether KD group shows reduced brain activation (Hypothesis 2), higher functional connectivity (Hypothesis 3), and prefrontal cortex atrophy and ventricular enlargement (Hypothesis 4) compared to the control diet group. Assuming $\alpha = 0.05$ and $\beta = 0.2$, the proposed sample sizes will allow us to detect an effect size of 0.9.

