consent process in accordance with NIH policy. Only subjects that can give informed consent will be included in this study. The PI and/or AI's will determine that the subjects are able to give informed consent based on their clinical assessment of the subject's ability to understand the nature of the study and the risks. If patient's BAL is more than 0 and/or if their CIWA is more than 8 at the time of consent, or if the subject's capacity to consent remains otherwise questionable, the Ability to Consent Assessment team (ACAT) will be consulted. HSPU advocates will monitor the informed consent discussion conducted between investigator and subject assessing subject capacity to enroll in the study and providing ongoing monitoring over the course of research participation. Co-workers will not consent each other if possible, but if a coworker does consent another, HSPU will monitor the consent process.

c. Consent documents

The consent form contains all required elements. The original consent is filed with their NIH medical record and a digital copy is uploaded into the CRIS system. A copy of the signed consent is also made for the subject's research binder for regulatory purposes.

14. Data and Safety Monitoring

a. Data and safety monitor

Data and safety monitoring will be monitored by the PI, who will review all safety data for each participant. The PI will consult with the Medically Accountable Investigator (MAI) should any concerns about safety arise.

b. Data and safety monitoring plan

This study will be monitored on a yearly basis at the time of continuing review. We will look at possible trends in AE's and UP's to determine if a change to the protocol/consent/study procedures becomes necessary via study amendment. In addition, individual subject case report forms will be monitored on an ongoing basis upon completion of study visits. Frequency of monitoring may increase if the PI determines it is necessary.

c. Criteria for stopping the study or suspending enrollment or procedures

This study will be stopped and enrollment suspended if any serious adverse events occur that is determined to potentially be related to one of the study procedures.

15. Quality Assurance (QA)

a. Quality assurance monitoring

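### If the KD:SA ratio is changed after the first 20 participants, the Hypothesis 1 t-test has no term for enrolment before or after the change (minor)

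*Combined protocol and SAP*

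**What the plan says.** Section 4.e.2 (Randomization and blinding) states that "A randomization code will be generated prior to recruiting and patient randomization will be assigned accordingly". Because more dropout is expected on KD, "we pre-set the ratio of KD:SA participants as 3:2 in the randomization generation". Then: "This ratio will be set for the first 20 participants". After that an independent nurse evaluates the ratio "based on diet compliance during their 3 weeks inpatient stay as per questionnaire and urine screen", and "Results are shared with the PI who will modify the ratio if needed to aim for a 50% KD versus 50% SA study completion". The section does not say how a changed ratio enters the list drawn up before recruitment. Nor does it say which ratio applies to people enrolled while the first 20 complete their three weeks.

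On analysis, section 10.b says of Hypothesis 1: "Independent sample t-test will be used to test" it. The note closing that section puts every patient with week-1 assessments into the test, so participants from before and after any change are pooled. Section 10.a names only addiction severity and age as possible covariates, and only if the groups differ on them. Mixed ANOVAs compare the diets for Hypotheses 2 to 4. No analysis mentions enrolment period or the ratio in force.

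**The concern.** Randomisation makes the arms comparable among people allocated under the same ratio. When the ratio changes, the arms hold different proportions of early and late participants. If outcomes differ between the periods for reasons unrelated to diet (who is referred, how detoxification is run, how diet coaching is done), an unadjusted comparison attributes part of that difference to diet. At stake is the first primary comparison, KD v SA on withdrawal symptoms. Two conditions must both hold: the ratio is changed, and outcomes drift.

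**Working it through.** **The plan's own figure.** Section 10.b recruits 100 to complete 50 at about 50% non-completion: 50 / (1 − 0.5) = 100. This reproduces.

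**Inputs from section 4.e.2.** A 3:2 ratio in the first 20 gives an expected 12 KD and 8 SA.

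**Assumptions, because the documents give no figure.**
- 100 participants are randomised. Section 3.a counts 100 as accrual and expects half to drop out or fail the criteria, so the number randomised is not stated.
- The later ratio is 1:1, 3:1 or 1:2 (KD:SA) for the remaining 80.
- The drift τ (mean of the first cohort minus mean of the later one, same diet) is 0.5 SD.

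**Formula.** With p_KD and p_SA the share of each arm that comes from the first 20, the bias of the unadjusted mean difference is (p_KD − p_SA) × τ.

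| Later KD:SA | Arm totals | p_KD | p_SA | Difference | Bias at τ = 0.5 SD |
|---|---|---|---|---|---|
| 3:2 (no change) | 60 / 40 | 12/60 = 0.200 | 8/40 = 0.200 | 0 | 0 |
| 1:1 | 52 / 48 | 12/52 = 0.231 | 8/48 = 0.167 | 0.064 | 0.03 SD |
| 3:1 | 72 / 28 | 12/72 = 0.167 | 8/28 = 0.286 | −0.119 | −0.06 SD |
| 1:2 | 38.7 / 61.3 | 12/38.7 = 0.310 | 8/61.3 = 0.130 | 0.180 | 0.09 SD |

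**Fewer randomised.** With 60 randomised and 1:1 after the first 20, the shares are 12/32 = 37.5% and 8/28 = 28.6%, and the bias is 0.089 × 0.5 = 0.045 SD.

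**Type I error.** In 40,000 simulated trials per scenario (two-sided 0.05, whole-number counts), the unadjusted t-test rejects a true null at rates of 0.048 (1:1), 0.055 (3:1) and 0.066 (1:2) when τ = 0.5. If τ is doubled to 1 SD, the rates are 0.044, 0.061 and 0.104, and the largest bias is 0.18 SD.

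**With a cohort term.** In the same simulations, and in the completer splits below, diet plus cohort gives bias of zero to within simulation error and type I error of 0.049 to 0.052.

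**Cost of the term.** By the noncentral t (two-sided 0.05, 80% power), 25 v 25 without the term detects 0.809 SD. This is a fresh calculation: section 10.b gives 0.66 and 0.9 alongside the paired tests and the mixed ANOVAs, and no separate figure for Hypothesis 1. Adding cohort multiplies the detectable effect by about 1/√(1 − φ²), where φ is the correlation of arm with cohort. Three assumed splits of 25 + 25 completers:
- 6 KD / 4 SA early, 19 / 21 late: φ = 0.10, detectable effect 0.813 SD.
- 3 / 6 early, 22 / 19 late: φ = −0.16, detectable effect 0.819 SD.
- 9 / 4 early, 16 / 21 late: φ = 0.23, detectable effect 0.831 SD.

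Left unadjusted at τ = 0.5, these splits carry biases of 0.04, −0.06 and 0.10 SD, the same order as the table.

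**The case against.** The strongest reply is that the harm is conditional and slight. The ratio moves only if needed. The 0.5 SD drift is an assumption with nothing in the documents behind it. Against the 0.66 and 0.9 in section 10.b, a bias of 0.03 to 0.09 SD is roughly 3% to 14%. The largest case, 1:2, would be called for only if KD participants completed about twice as often as SA participants, whereas section 4.e.2 expects more dropout on KD. For Hypotheses 2 to 4, a stable difference in level between cohorts cancels from the group-by-time contrast, so only drift in the change itself matters there. All of this stands, and it is why the point is minor. It does not remove the case for a term that costs almost nothing.

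A reader might go further and infer three things that the documents do not support.

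- **That the PI step materially weakens the blind.** The text says only that results are shared. That they are by arm is an inference, though a reasonable one. Section 4.e (Study Timeline) already breaks each individual's blind after the final MRI, so aggregate results on past participants add little and reveal no future allocation. For outcome raters, "Nurses and research staff who do CIWA, craving ratings and other study procedures with patients will not have access to the randomization key". The PI does review all safety data (section 14.a), but discretionary withdrawal in section 8 is shared with the Medical Investigator and tied to adverse-event severity.
- **That the ratio change has no stated rule or target.** Timing, data source, evaluator and target (equal completion) are all given. Only a numerical criterion is missing. A mechanical one would not clearly help: if true completion were 25/60 = 41.7% on KD and 25/40 = 62.5% on SA, so that 3:2 was already right, the ratio implied by completion among 12 and 8 people would run from 0.61 to 4.28 (5th to 95th percentile). It would fall below 1:1 or above 2:1 in 52% of simulated trials.
- **That this is an interim look at efficacy.** The review uses diet compliance, not outcomes.

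**Conclusion.** The gap holds in a limited form. The plan permits a ratio change and states a pooled Hypothesis 1 test with no adjustment for it. If the ratio was changed, the expected bias is about 0.03 to 0.09 SD in absolute size, assuming 100 randomised, later ratios of 1:1, 3:1 or 1:2 and a 0.5 SD drift. For a move to 1:1, type I error is not inflated. A material problem needs both a large change in ratio and a large drift. If the ratio was never changed, there is no bias from this source. Whether it was changed cannot be told from the documents. Severity: minor.

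**What to change.** In section 10, state that if the ratio was modified:

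- Hypothesis 1 is tested with a linear model of diet plus cohort (before or after the change) in place of the unadjusted t-test.
- The same between-subject factor, with its cohort-by-time interaction, is added to the KD v SA mixed ANOVAs.

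Define cohort by the ratio in force when the participant was randomised, because the switch may not fall exactly at participant 21. If the ratio was not modified, say so, and the t-test can stand. This can be adopted before analysis even if the 20-participant review has already taken place.

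The cost is a few sentences, one degree of freedom for a single change, and a detectable effect at 25 per arm that goes from 0.809 to at most 0.831 SD in the splits examined.

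Optionally, section 4.e.2 could have the independent key-holder issue the revised list without passing results by arm to the PI. That needs no extra staff, since this person already makes the evaluation.

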Procedures	Week 1	Week 2	Weeks 3-4
KD/SA Randomization (solid food and shake) 3 snacks and 3 shakes p/day until stopped – up to 4 weeks while inpatient	x	x	x
Neuropsychological test battery (NPT)	x		x
Personality tests	x		
MRI Scan session (structure, functional reactivity, functional connectivity, MRS) ~ 3 hrs	x	x	x
Sleep Profiler	2x	2x	2x

TMGENEActive (actigraphy) – full week	x		X
Urine tests for ketones	Daily	Daily	Daily
Finger pricks for ketones	up to 5x	up to 5x	up to 5x
Blood tests for ketones and ghrelin	2x	1x	1x
Blood tests for fatty acids, liver function, platelets and coagulation	1x	1x	1x

Time points are targets, and the order can be adjusted for practical considerations during the inpatient stay.

Upon discharge from the NIH CC, participants in the study will be followed up for 3 months. For this purpose, we will call the participants by phone at weeks 1, 2, 4, 8 and 12 to ask questions about relapse and sobriety. This will take about 5 minutes or less. The following questions which are from the Alcohol Timeline Follow Back (ATFB) will be asked during the follow up:

- i. In the last 7 days, did you drink any alcohol?; Y ___ N ___
- ii. If yes we then ask “On what days did you drink”?; and
- iii. How much did you drink?

b. Recruitment

Participants will be recruited through referrals from the NIH Volunteer Office, the Patient Recruitment and Public Liaison (PRPL) Office, the NIAAA Intramural Research Program screening protocol 14-AA-0181 and through ResearchMatch.org and www.craigslist.com.

Participants (including NIH employees with an AUD) will also be recruited by word of mouth and through IRB-approved local advertisements. There will be no direct solicitation of employees by supervisors or coworkers. These will include: (1) Flyers posted on NIH campus, campuses of universities and colleges, public places and public transportation services in the greater Washington DC area; (2) Advertisements in electronic and printed local media (newsletters, websites including www.niaaa.nih.gov/join-study#, researchstudies.drugabuse.gov, newspapers including the Baltimore Beat, Baltimore Sun, the Beacon, Washington City Paper, Streetsense, the Express, craigslist.org, NIH and other local email distribution lists), following IRB approval, (3) through substance abuse treatment programs of clinics (e.g. Caron Treatment Facilities).

ClinicalTrials.gov may also represent a source of recruitment.

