To measure the effectiveness of the ketogenic diet in increasing ketone bodies, we will measure ketones in urine daily as recommended for monitoring ketogenic diets in the management of epilepsy [70]. Specifically, we will measure acetoacetate (AA) in urine, in the early morning starting the day after initiation of the KD diet or the control diet and every day thereafter. We will use over-the-counter reagent strips (Ketostix, Bayer Vital GmbH, Leverkusen, Germany), which determine the presence of AA. Moreover,

beta-hydroxybutyrate (BHB) will be measured up to 5 times per week with a finger prick (Precision xtra, Abbott).

We will also measure beta-hydroxybutyrate and acetoacetate in blood at baseline and once each study week and free fatty acids once per week (no more than 8mL per week). These measures will be associated with MRS measures (e.g., correlate beta-hydroxybutyrate and acetoacetate in blood with β -hydroxybutyrate and acetone concentrations in the anterior cingulate and frontal white matter), and will provide information on potentially unwanted consequences of KD (e.g., potential disturbing effect of KD on free fatty acid concentrations). If the Laboratory of Medicine at the Clinical Center cannot provide quantitative measures for beta-hydroxybutyrate and acetoacetate, assays will be used from Wako Chemicals GmbH, Neuss, Germany). We will also measure plasma ghrelin (up to 6cc) at baseline and on a weekly basis.

Weekly blood draws are scheduled to monitor liver function (2.5 cc), platelet counts (2cc) and coagulation (INR, 3cc).

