- b. Ketogenic diet (KD): Ketogenic diets are not recommended in patients with urolithiasis, liver disorders, cardiomyopathy and chronic metabolic acidosis [67]. Despite being a controversial treatment, the ketogenic diet has been studied as a treatment aid for dyslipidemia, obesity diabetes, epilepsy, brain tumors, autism, and neuroprotection with positive results. We will exclude participants with a history of urolithiasis and liver disorders other than mild alcoholic hepatic changes to decrease the risk to the participants. Liver function will be monitored during the study on a weekly basis as it is standard during the detox and treatment of alcoholism. The diet will be discontinued if there is a progression of liver damage after the detox is completed (3-5 x the upper-bound limit). KD may also have potential side effects, including GI discomfort and constipation, dyslipidemia, and low platelet counts and coagulation problems. Platelet counts and coagulation will be monitored on a weekly basis and the diet will be discontinued if platelet count < 100,000 or INR > 1.5. Free fatty acid levels in blood will also be monitored on a weekly basis. To facilitate compliance and decrease the burden on the participants the diet will consist of a primarily liquid diet (house-made by Nutrition Department), in combination with ketogenic solid snacks (e.g., eggs, meat, fish, vegetables). The meals will be provided after an assessment with the nutritionist. Most of our treatment seeking alcohol dependent subjects have chronic problems with malnutrition and have a very poor intake of solids while they drink. Therefore, the liquid diet was considered a better option to improve compliance. An additional benefit is that it provides a way to make patients unaware of whether they are in the ketogenic- or control diet group. We will measure ketones on a weekly basis for diet compliance. If a subject is withdrawn from the study for non-compliance to the diet, he/she will be paid for procedures completed up to the point of withdrawal.
- c. Venous line placements: Subjects may have some discomfort and bruising from the needle insertion. Some people feel light-headed or faint. The risks of an

intravenous catheter also include bleeding, infection, or inflammation of the skin and vein with pain and swelling. These will be treated if they occur.

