- d. *Blood sampling*: Blood draw volumes will not exceed the limits allowed by the NIH Clinical Center (Medical Administrative Policy 95-9: Guidelines for Limits of Blood Drawn for Research Purposes in the Clinical Center: http://internal.cc.nih.gov/policies/list_policies.asp?index=med_chrono). Blood sampling may lead to the formation of a small subcutaneous hematoma caused by blood leaking from a punctured blood vessel. This hematoma causes only minor discomfort. It is not dangerous and requires no treatment other than reassuring the patient. There is also a small risk of infection at the site of the needle puncture, which can be readily treated with antibiotic therapy. Subjects will be asked not to donate blood for a period of eight weeks after the participation is completed. The approximate amount of blood drawn in this protocol is as follows: Screening labs: 30 cc (obtained under 14-AA-0181); and Genotyping: 10 cc; plus up to 48 cc for research purpose to measure free fatty acid and ketone concentrations, 24 cc for ghrelin, and up to 23 cc for weekly liver function, platelet count and coagulation. Total amount over course of study not to exceed 140 cc.
- e. *MRI Risks*: People are at risk for injury from the MRI magnet if they have pacemakers or other implanted electrical devices, brain stimulators, some types of dental implants, aneurysm clips (metal clips on the wall of a large artery), metallic prostheses (including metal pins and rods, heart valves, and cochlear implants), permanent eyeliner, implanted delivery pump, or shrapnel fragments. Welders and metal workers are also at risk for injury because of possible small metal fragments in the eye of which they may be unaware. Subjects will be screened for these conditions before having any scan, and if he/she has any, he/she will not receive an MRI scan. If a subject has a question about any metal objects being present in his/her body, he/she should inform the staff. In addition, all magnetic objects (for example, watches, coins, jewelry, and credit cards) must be removed before entering the MRI scan room.

It is not known if MRI is completely safe for a developing fetus. Therefore, all women of childbearing potential will have a pregnancy test performed no more than 24 hours before each MRI scan. The scan will not be done if the pregnancy test is positive.

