NIH guidelines on conflict of interest have been distributed to all investigators.

b. Conflict of interest

There are no conflicts of interest to report.

c. Role of a commercial company or sponsor

There is no drug company involved.

21. Technology Transfer

This study now has two separate data transfer agreements (DTA's) in place under the following docket numbers:

1. AA DTA 22-11002: This DTA is between UPENN and NIAAA/LNI. We will send deidentified (coded) MRI imaging data for further analysis which includes: MRS and fMRI time series and associated data as well as craving data in response to alcohol cues from the fMRI scan sessions to our collaborator at UPENN for analyzation. UPENN will send back the results and we will match it back up to the subjects on our end.
2. AA DTA 22-11006: This DTA is between Zhejiang University, China, and NIAAA/LNI. We will send coded MRI imaging data for further analysis which includes: fMRI resting state time series and associated data as well as craving data in response to alcohol cues from the fMRI scan sessions to Zhejiang University China, for analysis. Zhejiang University will send back the results and we will match it back up to the subjects on our end.

22. Research and Travel Compensation

Volunteers will be compensated for time and research-related inconveniences, to the extent to which they complete them, as follows:

Procedures	Inconvenience Units	\$ Payment	Frequency	Total
Week 1 Study Procedures				
KD/SA Randomization Week	10	100	1	100
Genetics blood draw	1	10	1	10
Urine Drug Screen prior to MRI/NPT	1	10	1	10
Saliva Drug Screen prior to MRI/NPT	1	10	1	10
Urine pregnancy if female who can become pregnant prior to MRI/NPT	1	10	1	10
Ketone blood test #1 – obtained prior to start of KD/SA start	1	10	1	10
Ghrelin blood test #1 – obtained prior to start of KD/SA start	1	10	1	10
MRI session #1 (structure, functional reactivity, functional connectivity, MRS)	10	100	1	100
Neuropsychological Test Battery and Personality tests (NPT) including questionnaires Session #1	13	130	1	130

Sleep Profiler #1	10	100	1	100
Sleep Profiler #2	10	100	1	100
TMGENEActiv #1 (entire week of wear)	10	100	1	100
Ratings for Mood, Sleep, and Alcohol Craving	7	70	daily	total of 70
Daily urine ketone test	1	10	daily	total of 70
Ketone finger prick	1	10	Up to 5x/week	max of 50
Ketone blood test #2	1	10	1	10
Ghrelin blood test #2	1	10	1	10
Liver function, FFA platelets/coagulation blood test #1	1	10	1	10

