Week #1 – Total Compensation up to				\$910

Week 2 Study Procedures

KD/SA Randomization Week 2	10	100	1	100
Urine Drug Screen prior to MRI	1	10	1	10
Saliva Drug Screen prior to MRI	1	10	1	10
Urine pregnancy if female who can become pregnant prior to MRI	1	10	1	10
MRI session #2 (structure, functional reactivity, functional connectivity, MRS)	10	100	1	100
Sleep Profiler #3	10	100	1	100
Sleep Profiler #4	10	100	1	100
Ratings for Mood, Sleep, and Alcohol Craving	7	70	daily	total of 70
Daily urine ketone test	1	10	daily	total of 70
Ketone finger prick	1	10	Up to 5x/week	max of 50
Ketone blood test #3	1	10	1	10
Ghrelin blood test #3	1	10	1	10
Liver function, FFA, platelets/coagulation blood test #2	1	10	1	10
Week #2 – Total Compensation up to				\$650
Week 3 Study Procedures				

KD/SA Randomization Week	10	100	1	100
Urine Drug Screen prior to MRI/NPT	1	10	1	10
Saliva Drug Screen prior to MRI/NPT	1	10	1	10
Urine pregnancy if female who can become pregnant prior to MRI/NPT	1	10	1	10
MRI session #3 (structure, functional reactivity, functional connectivity, MRS)	10	100	1	100
NPT including questionnaires Session #2 (Personality Measures will not be repeated)	13	130	1	130
Sleep Profiler #5	10	100	1	100
Sleep Profiler #6	10	100	1	100
TM GENEActiv #2 (entire week of wear)	10	100	1	100
Ratings for Mood, Sleep, and Alcohol Craving	7	70	daily	total of 70
Daily urine ketone test	1	10	daily	total of 70
Ketone finger prick	1	10	Up to 5x/week	max of 50
Ketone blood test #4	1	10	1	10
Ghrelin blood test #4	1	10	1	10
Liver function, FFA, platelets/coagulation blood test #3	1	10	1	10
Week #3 – Total Compensation up to				\$880
Potential Week 4 Study Procedures				
♦KD/SA Randomization Week	10	100	1	100
Week #4 – Total Compensation up to				\$100
Total Compensation to all subjects up to paid on discharge				\$ 2540
Telephone Follow-Ups				
Week 1 post discharge	1	10	1	10

Week 2 post discharge	1	10	1	10
Week 4 post discharge	1	10	1	10
Week 8 post discharge	1	10	1	10
Week 12 post discharge	1	10	1	10
Total Compensation for F-Ups				50
Total Compensation to all subjects up to paid on discharge				\$ 2590

♦ Note that if KD continues into Week 4, subjects will be compensated.

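### Weekly safety draws drive the diet-stopping limits and the diet may run four weeks, but the tables and blood budget provide only three draws

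*Combined protocol and SAP*

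**What the plan says.** **Monitoring and limits.** Section 7.b says: "Platelet counts and coagulation will be monitored on a weekly basis and the diet will be discontinued if platelet count < 100,000 or INR >" (the INR limit is 1.5). The same section promises weekly liver function tests and gives a liver limit for ending the diet. Section 4.e.1 repeats the frequency and gives the volumes: "Weekly blood draws are scheduled to monitor liver function (2.5 cc), platelet counts (2cc) and coagulation (INR, 3cc").

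**Permitted exposure.** Section 3.a allows the study food and shakes for up to four weeks. The procedures table in Section 4.a says "3 snacks and 3 shakes p/day until stopped – up to 4 weeks while inpatient". The compensation table in Section 22 has a block headed "Potential Week 4 Study Procedures" and pays for the diet in that week.

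**Planned end of diet.** Section 4.e stops the diets after the final MRI session, which it places in the third week of hospitalization.

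**Draws provided.** In the procedures table, the row "Blood tests for fatty acids, liver function, platelets and coagulation" shows one draw in week 1, one in week 2 and one in a single column covering weeks 3 and 4. The compensation table numbers these tests 1, 2 and 3 under weeks 1, 2 and 3; its week-4 block lists only the diet payment. Section 7.d budgets "up to 23 cc for weekly liver function, platelet count and coagulation" within an overall ceiling of 140 cc.

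**The concern.** The platelet, INR and liver values are the laboratory limits at which the protocol ends the diet for safety, and such a limit works only while the test behind it is being done. The monitoring text promises a test in each week and the exposure text permits four weeks, but the operational parts of the plan appear to have been built for three. Staff who follow the tables would leave one permitted diet week untested, and staff who add the missing test would exceed the protocol's own blood ceiling when the other lines are used in full. Safety review is by the investigator, with no data and safety monitoring board, so the scheduled tests carry much of the protection.

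**Working it through.** **Inputs**

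| Item | Value | Source |
|---|---|---|
| Volume per safety draw | 2.5 + 2 + 3 cc | Section 4.e.1 |
| Budget for safety draws | 23 cc | Section 7.d |
| Screening labs | 30 cc | Section 7.d |
| Genotyping | 10 cc | Section 7.d |
| Ketones and free fatty acids | up to 48 cc | Section 7.d |
| Ghrelin | 24 cc | Section 7.d |
| Ceiling | 140 cc | Section 7.d |
| Longest diet | 4 weeks | Sections 3.a, 4.a, 22 |

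**Step 1: reproduce the plan's figure.** One draw is 2.5 + 2 + 3 = 7.5 cc. Three draws are 3 × 7.5 = 22.5 cc, which rounds to the stated 23 cc. Four draws are 4 × 7.5 = 30 cc, which does not fit. The budget was therefore built on three draws, in agreement with both tables. The ghrelin line fits the same pattern: at up to 6 cc per sample (Section 4.e.9), 24 / 6 = 4 samples, that is, baseline plus three weeks.

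**Step 2: compare draws with diet weeks.** Weekly testing over four weeks needs four draws, and three are provided, so 4 − 3 = 1 diet week has none. That is up to 7 of 28 days, or 25% of the longest permitted exposure. Which week it is depends on the table. The compensation table leaves week 4 without a draw. The merged column in the procedures table lets the third draw fall in week 3 or week 4, and the other week then has none.

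**Step 3: total blood volume.**

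- As stated: 30 + 10 + 48 + 24 + 23 = 135 cc, within 140.
- With a fourth safety draw: 30 + 10 + 48 + 24 + 30 = 142 cc, which is 2 cc over.

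**Step 4: how firm is the 142 cc?** It takes every other line at its stated maximum. Section 4.e.1 gives "free fatty acids once per week (no more than 8mL per week"), and it is unclear whether that bound covers ketones as well. If it does, the 48 cc line would be 4 × 8 = 32 cc for four draws or 5 × 8 = 40 cc for five; 48 cc corresponds to six. The four-draw total would then be:

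- 30 + 10 + 32 + 24 + 30 = 126 cc, or
- 30 + 10 + 40 + 24 + 30 = 134 cc.

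If ghrelin also gets a fifth sample (30 cc), the 134 becomes 140 cc and the 142 becomes 148 cc. Whether a fourth draw fits under the ceiling thus depends on lines that the documents do not settle: the range is 126 to 148 cc.

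**The case against.** **The planned course has no gap.** This is the strongest objection, and it stands. If the diet ends after a third-week MRI, three draws are weekly. Week 4 is only a possibility, and the documents do not say how many patients reach it. It is nonetheless foreseeable. The procedures table puts the last MRI in the weeks 3-4 column, Section 3.c sets no limit on rescheduling after a positive alcohol or drug screen, and Section 4.e.4 allows a repeat scan session.

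**The schedule is flexible.** The table's footnote treats time points as targets. That lets a draw be moved, but it does not supply a fourth.

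**The payment table is weak evidence.** Its week-4 block also omits the daily urine ketone test, so its silence does not prove that a test is not done. A reader might infer that no safety test can occur in week 4, or that the limits cannot be applied at the end of exposure. The documents do not support that: the merged column allows the third draw to fall in week 4, and Section 7.b describes weekly liver tests as usual care during detoxification and treatment. What remains is that testing in every diet week is not assured.

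**Further inferences that should not be drawn.**

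- *A missing pre-diet INR.* The compensation table has "Ketone blood test #1 – obtained prior to start of KD/SA start", while the first safety test carries no such note, and the screening labs listed in Section 4.d name no INR. But no section promises a pre-diet INR, so none is contradicted, and eligibility testing runs under a separate protocol that is not in these documents.
- *An error in the 48 cc.* The 8 mL bound can be read as applying to free fatty acids alone. Three such draws would use 3 × 8 = 24 cc, leaving 24 cc for four ketone draws at 6 cc each (an assumption, since no ketone volume is stated). The two figures need explaining, but 48 cc is not shown to be wrong.
- *Assured room under the ceiling.* Step 4 of the working shows that this holds on some readings and fails on others.

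**Conclusion.** The inconsistency is real and limited in scope. Weekly tests are promised, four weeks of diet are permitted, and three draws are provided. For a patient who continues into week 4, one diet week of up to seven days has no scheduled draw, and application of the stopping limits in that week is not assured. The gap is firmest for platelets and INR; for liver function it may be filled by usual care. A patient whose diet ends after a third-week MRI is not affected.

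The three-draw finding rests on simple arithmetic that reproduces the stated 23 cc, and on two tables that agree with it. The excess over the ceiling (142 against 140 cc) holds with the other blood lines at their stated values. The number of patients affected is unknown.

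**What to change.** Reconcile Sections 3.a, 4.a (procedures table), 4.e, 4.e.1, 7.b, 7.d and 22 so that they agree on:

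- how long the diet may run, and how that relates to stopping after the final MRI;
- how many safety draws there are and in which weeks they fall, including whether weeks 3 and 4 share one;
- the blood-volume lines and the ceiling.

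In the same amendment, state how the 48 cc in Section 7.d relates to the 8 mL weekly bound in Section 4.e.1. The sponsor decides which way each mismatch is resolved; this point does not favour a particular diet duration, test schedule or limit.

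The cost is an amendment to two tables and the blood-volume paragraph, with matching wording elsewhere. If a draw is added, it is at most one 7.5 cc sample for each patient on diet in week 4, already covered by the promise of weekly testing. These patients are inpatients, so no visit is added.
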